4.10.2. Clinical Laboratory Evaluations

Hematology laboratory assessments will include white blood cell count with differential, hemoglobin, hematocrit, mean corpuscular volume, mean corpuscular hemoglobin, mean corpuscular hemoglobin concentration, total red cell count with morphology, and platelet count. These parameters will be measured at all study visits.

Biochemistry laboratory assessments will include sodium, potassium, chloride, bicarbonate, blood urea nitrogen, creatinine, magnesium, calcium, phosphorus, uric acid, glucose, total protein, albumin, globulin, albumin:globulin ratio, bilirubin (total, direct and indirect), creatine kinase (CK), lactate dehydrogenase (LDH), alanine aminotransferase (ALT), aspartate aminotransferase (AST), gamma glutamyl transferase (GGT), alkaline phosphatase, total cholesterol, high-density lipoprotein (HDL), low-density lipoprotein (LDL), triglycerides, and cystatin C. These parameters will be measured at all study visits. Ideally, subjects should have fasted for at least 8 hours prior to blood collection.

Urinalysis assessments will include pH, specific gravity, glucose, ketones, blood, protein, creatinine, urobilinogen, bilirubin, nitrite, and leukocyte esterase. These parameters will be measured at all study visits.

Hematology, serum biochemistry, and urinalysis data and their changes from baseline (only for continuous laboratory parameters) will be summarized by visit. Maximal and minimal change from baseline in each parameter will also be summarized.

Shift tables for hematology, serum biochemistry, and urinalysis will also be presented showing change in CTCAE severity grade from baseline to each visit. For parameters for which a CTCAE scale does not exist, shift tables will be presented showing change in results from baseline (normal, low, and high [or abnormal]) to each visit (normal, low, and high [or abnormal]).

Frequency tables will be presented for safety monitoring parameters to show the number and percentages of subjects by severity grade categories defined in Table 2. If a CTCAE grade does not exist, abnormal results will be summarized by protocol-defined thresholds as noted in Table 2. Subjects will be characterized only once for a given assay, based on their worst severity grade observed during the time period of interest.

As necessary, laboratory abnormalities will be described by duration of study drug exposure, by dose, by age group, by sex, by race, by weight, and for special populations (eg, antibiotic use).

Table 2. Safety Monitoring Parameters and Actions To Be Taken

| Organ System and Laboratory Parameter | Stop Study Drug Immediately, Confirm Abnormal Value, and Then Start Work-Up ^a | Stop Study Drug After Confirming Abnormal Value, and Then Start Work-Up ^a | Continue Study Drug, Confirm Abnormal Value, and then Start Work-Up ^a | |
|--|---|--|--|--|
| Hepatic | | | | |
| Serum total bilirubin ^b | ≥Grade 3 (≥3.0 x ULN) | Grade 2 (1.5 – 3.0 x ULN) | | |
| Serum ALT | ≥Grade 3 (≥5.0 x ULN) | Grade 2 (>2.5 – 5.0 x ULN) | | |
| Serum AST | ≥Grade 3 (≥5.0 x ULN) | Grade 2 (>2.5 – 5.0 x ULN) | | |
| Serum GGT | ≥Grade 3 (≥5.0 x ULN) | Grade 2 (>2.5 – 5.0 x ULN) | | |
| Renal | | | | |
| Serum cystatin C | >2.00 mg/L | >1.33 – 2.00 mg/L | | |
| Serum creatinine | ≥ Grade 2 (≥1.5 x ULN for age) | Grade 1 (>ULN – 1.5 x ULN for age) | | |
| Serum BUN | ≥3.0 x ULN | ≥1.5 – 3.0 x ULN | | |

^a Laboratory abnormalities may be confirmed immediately or at the next scheduled clinic visit based on investigator judgment.

Abbreviations: ALT = alanine aminotransferase, AST = aspartate aminotransferase, BUN = blood urea nitrogen, GGT = gamma glutamyl transferase, ULN = upper limit of normal

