11.4.6. Secondary Variables

11.4.6.1 Spirometry

Both absolute change and relative change in %-predicted FEV_1 from Baseline at each visit will be summarized descriptively. Pediatric equations for calculating %-predicted FEV_1 [Wang 1993] will be used from 6 to <16 years of age for female subjects and from 6 to <18 years of age for male subjects. For males or females >18 years of age, an adult equation for calculating %-predicted FEV_1 [Hankinson 1999] will be used. Each %-predicted FEV_1 will be based on the height value obtained at the same study visit. The changes from baseline to each post-baseline visit will be analyzed using paired t-tests.

Above analyses will be repeated for FVC and FEF₂₅₋₇₅.

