14.1.2 Reproductive Considerations

Ataluren is not genotoxic, did not affect fertility in male and female rats, and was not teratogenic in rats and rabbits. In addition, lack of sexual maturity in many of the patients likely to be enrolled in this study limits reproductive risks. However, restriction on eligibility relating to willingness to avoid unprotected sexual intercourse in any patients known to be sexually active is included as a general precaution. Because it is unknown if ataluren is excreted in breast milk, lactating female patients who are breast-feeding are excluded from participation.

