- Serum Creatinine: Given the widespread clinical familiarity with serum creatinine as a marker of renal dysfunction and as a monitoring tool for nephrotoxins in clinical practice [Gilead 2002, Gilead 2006, Novartis 2005], characterization of serum creatinine provides an appropriate frame of reference relative to other experiences.
- Serum Cystatin C: An alternative to assessing GFR based on serum creatinine, serum cystatin C offers advantages in the assessment of renal function in the context of this protocol. Cystatin C is a low-molecular-weight {~13 kDa} proteinase inhibitor derived from all cells that is filtered by the glomerulus and degraded in the renal tubules [Herget-Rosenthal 2007]. The serum cystatin C concentration is almost solely dependent upon GFR and appears relatively unaffected by muscle mass or other conditions. An additional advantage is that circulating cystatin C changes more rapidly in response to multiple types of renal injury than creatinine [Herget-Rosenthal 2007]. Methods for measuring cystatin C are standardized and the correlations between serum cystatin C and GFR have been derived and confirmed in large studies involving healthy children and adults and those with renal dysfunction [Dharnidharka 2002, Grubb 2005, Zappitelli 2007]. Based on these considerations, values of serum cystatin above 1.33 mg/L should prompt diagnostic evaluation and interruption/modification of study drug if required per protocol.

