In addition, in clinical trials in nmDMD the adverse-event profile of ataluren was comparable to that of placebo. In the double-blind Phase 2b study of nmDMD, six patients – all receiving corticosteroids - had hypertension (or increased blood pressure) reported as adverse events (0 for ataluren 20-, 20-, 40-mg/kg, 5 for ataluren 10-, 10-, 20-mg/kg, and 1 for placebo), although similar events were not seen in the nmCF studies. Mean total cholesterol and triglycerides were in the upper range of normal at baseline and increased, reaching borderline high or high values. The values tended to stabilize early in the study and did not increase further with continued treatment. Small increases in mean serum creatinine, BUN, and cystatin C were observed. Similarly, the values tended to stabilize early in the study and did not increase further with continued treatment.

Collectively, the safety data from clinical trials demonstrate that ataluren has a favorable safety profile for the treatment of patients with nmCF.

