2. STUDY OVERVIEW

2.1. Study Design

Study 021e is a Phase 3, international, multicenter, open-label, extension study of ataluren in patients with nmCF that have completed participation in the double-blind study PTC124-GD-021-CF (Study 021).

All eligible patients that completed participation in Study 021 will be enrolled into the study. Eligible subjects will receive oral ataluren administered 3 times per day (TID) at respective morning, midday, and evening doses of 10-, 10-, and 20-mg/kg for 96 weeks. The detailed schedule of assessments are displayed in Table 1.

Screening and baseline procedures are structured to avoid a gap in treatment between the double-blind study (PTC124-GD-021-CF) and this extension study. When possible, Screening/Baseline (Visit 1) for this extension study should occur on the same day as the End-of-Study visit for the double-blind study (PTC124-GD-021-CF). During the treatment period, study assessments will be performed at clinic visits at Week 12 and thereafter every 12 weeks until the end of the study.

Planned interim safety analyses will be conducted by an independent data monitoring committee (DMC). The first safety review will occur when ~ 100 patients have completed >=36 weeks of treatment. The second safety review will occur when ~ 100 patients have completed >=72 weeks of treatment.

The study will be terminated prematurely according to company's strategic decision on March 2, 2017. All subject who are on-going by then will be discontinued.

Table 1. Schedule of Events

| Study Period | Screening/B aseline | Treatment Period | | | | | | Post-Treatment | | |
|---|---------------------|------------------|----|----|----|----|----|----------------|-----------------------------|--------------------|
| Study Week (±7 days) | Day 1 | 12 | 24 | 36 | 48 | 60 | 72 | 84 | End of Tx/ Premature D/C 96 | 4 Weeks Post-Tx |
| Visit | 1 | 2 | 3 | 4 | 5 | 6 | 7 | 8 | 9 | 10 |
| Informed consent | X | | | | | | | | | |
| CFQ-R administration | X ^a | X | X | X | X | X | X | X | X | |
| Vital signs | Xa | X | X | X | X | X | X | X | X | X |
| Height | X ^a | X | X | X | X | X | X | X | X | X |
| Weight | X ^a | X | X | X | X | X | X | X | X | X |
| Physical examination | X ^a | | | | X | | | | X | X |
| Hematology | X ^a | X | X | X | X | X | X | X | X | X |
| Biochemistry | X ^a | X | X | X | X | X | X | X | X | X |
| Urinalysis | Xa | X | X | X | X | X | X | X | X | X |
| Renal ultrasound | Xa | | | | X | | | | X | |

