4.10. Primary Analyses

All primary analyses will be performed for the As-Treated population.

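### By-visit creatinine change is raw, pooled over children and adults, and uncontrolled, so that table alone cannot separate growth from a small drug effect

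*SAP*

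**What the plan says.** SAP 2.1 describes the design: "Study 021e is a Phase 3, international, multicenter, open-label, extension study of ataluren in patients with nmCF". There is no concurrent control. SAP 4.10 puts the laboratory data among the primary analyses and states "All primary analyses will be performed for the As-Treated population".

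For haematology, serum biochemistry and urinalysis, SAP 4.10.2 says "data and their changes from baseline (only for continuous laboratory parameters) will be summarized by visit". SAP 4.1 adds a mean, standard error and 95% confidence interval to each continuous summary. Nothing fixes an age split or an age-scaled version of creatinine change. The one provision on age is "As necessary, laboratory abnormalities will be described by duration of study drug exposure, by dose, by age group", which is conditional and concerns abnormalities.

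The same section also plans:
- frequency tables on the Table 2 categories, whose creatinine cut-offs are set on the ULN for age;
- shift tables by CTCAE grade;
- the same by-visit change summary for cystatin C and BUN.

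On the age range, Protocol 11.4.6.1 applies paediatric spirometry equations "from 6 to <16 years of age for female subjects and from 6 to <18 years of age for male subjects" and an adult equation at older ages. Protocol 14.1.2 expects "lack of sexual maturity in many of the patients likely to be enrolled in this study".

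**The concern.** The documents themselves treat creatinine as dependent on age and muscle mass. Table 2 refers it to the ULN for age. Protocol 14.2.4 favours cystatin C because it is "almost solely dependent upon GFR and appears relatively unaffected by muscle mass or other conditions". A growing child's creatinine can therefore be expected to rise whatever the drug does.

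The SAP allows for growth in other measures: paediatric blood pressure is read against height- and age-specific nomograms (SAP 4.12.1), weight and height of minors against growth-chart percentiles (SAP 4.12.2), and FEV₁ is expressed as percent predicted (SAP 4.11.1). The by-visit creatinine change has no such treatment, although the kidney is a main safety interest of the programme.

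Two misreadings are possible. A growth-related rise could be reported as a small mean increase on ataluren, or a small drug-related increase could be put down to growth. In Study 009 the conclusion that there was no cumulative renal effect rested on comparison with placebo at Week 48 (Protocol 14.2.4). The extension has no such comparison.

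**Working it through.** **1. Plan figure.** There is none to reproduce. SAP 2.4 bases the sample size on no hypothesis, and no standard deviation or target difference for creatinine is given.

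**2. Why the pooled table is ambiguous.** Let s be the share under 18, g the yearly growth-related rise in minors, t the years on study and d the mean drug effect, taken as equal in both age groups. Assume no growth-related rise in adults.
- Pooled mean change = s·g·t + d. This is one number with two unknown parts.
- Under 18: g·t + d. At 18 or over: d. The split separates them under these assumptions.

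**3. Follow-up actually available.** First dosing in Study 021 was on 15 August 2014 (Protocol 1). Adding 48 weeks gives 17 July 2015. Termination is set at 2 March 2017 (SAP 2.1), 594 days later: 594/7 = 84.9 weeks at most. The estimated 14-month recruitment (Protocol 1) is about 61 weeks, so the last entrants could have about 85 − 61 = 24 weeks and the midpoint is about 54 weeks. This assumes direct rollover and uniform recruitment to plan. Only the earliest entrants reach Week 84.

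**4. Illustrative drift with no drug effect.** The inputs are assumptions, not document figures: s = 0.30 to 0.60 and g = 0.02 to 0.05 mg/dL per year. Per year, s·g runs from 0.30 × 0.02 = 0.006 to 0.60 × 0.05 = 0.030 mg/dL.

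| Time | Years (weeks × 7/365.25) | Pooled drift, mg/dL |
|---|---|---|
| Week 48 | 0.920 | 0.006 to 0.028 |
| 54 weeks (midpoint) | 1.035 | 0.006 to 0.031 |
| Week 84 (earliest entrants) | 1.610 | 0.010 to 0.048 |

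**5. Against the precision of the mean.** The 95% half-width is 1.96 × SD/√n. The SD of change is assumed to be 0.08 to 0.15 mg/dL. For n, 100 is the interim-review trigger and 279 the upper bound in SAP 2.4.
- SD 0.08, n = 279: 1.96 × 0.08/√279 = 0.009.
- SD 0.15, n = 100: 1.96 × 0.15/√100 = 0.029.

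Drift and half-width are of the same order. Over part of the assumed range, growth alone would give an interval that excludes zero; over the rest it would not.

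**6. What the threshold tables catch.** The values here are chosen only to show the mechanism.
- Growth: a child at 0.63 mg/dL with a ULN of 0.70 has a ratio of 0.90. If both rise in step, to 0.72 and 0.80, the ratio stays at 0.90 while the raw change is +0.09. The age-referenced categories ignore the growth, as they should. Against the old ULN the ratio would be 0.72/0.70 = 1.03.
- Drug shift below the limit: 0.60 with a ULN of 0.80 is a ratio of 0.75. After +0.05 it is 0.65/0.80 = 0.81. The category does not change, so the shift shows only in the mean change.

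The renal listing in SAP 4.10.1 uses 1.5 times the ULN without saying that the limit is for age.

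**The case against.** A reader might infer that renal toxicity cannot be told apart from growth anywhere in this study. The documents do not support that. The Table 2 categories are age-referenced. Cystatin C has its own by-visit change and threshold summaries. BUN, CTCAE shift tables, renal adverse event tables and listings, and ultrasound shift tables are planned too. In Study 009 the serious renal events were graded creatinine elevations that resolved over days to weeks, all with potentially nephrotoxic antibiotics. Such events would be caught by these routes.

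A reader might also take the Duchenne experience as proof of a steady rise. Protocol 15.3 does say "Small increases in mean serum creatinine, BUN, and cystatin C were observed", but it adds that values levelled off early and did not climb further with continued treatment. That differs in shape from growth drift, and cystatin C moved as well, so the planned cystatin C table should help to show an effect of that kind.

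A third inference is that the age mix shifts from visit to visit as patients leave. Late-visit losses follow largely from the termination date and so track enrolment date. Nothing in the documents ties enrolment date to age.

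It is also fair that this is one descriptive table with no test or decision rule (SAP 4.2), and that the primary endpoint names laboratory abnormalities rather than mean change.

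What remains is narrow. The mean-change table is where a shift below the ULN would show. No joint reading with cystatin C is specified, and the age provision neither is fixed nor covers change.

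**Conclusion.** The point holds for the by-visit creatinine change table and no further. From that table alone, a growth-related rise and a small drug effect cannot be separated. The age-referenced categories and cystatin C give partial protection and leave the main route for detecting acute renal events intact.

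The size of the drift cannot be derived from the documents: neither the share of minors, nor the growth-related rise, nor the SD of change is given. The illustration of 0.006–0.028 mg/dL at Week 48 shows only that drift comparable with the confidence interval half-width is plausible under the assumed ranges. Severity is minor.

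**What to change.** In SAP 4.10.2, prespecify that creatinine change from baseline by visit is shown separately for patients under 18 and 18 or over at baseline, the age category already defined in SAP 4.6. Show it both in raw units and as a multiple of the ULN for age, beside the cystatin C change for the same groups. Estimated GFR is optional; the point does not depend on it.

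The cost is programming and a few extra descriptive tables, because the data and the age category already exist. SAP 1 allows refinements by amendment before database lock. There are two drawbacks: groups per cell are smaller, so intervals are wider; and if the laboratory's limits for age are set in broad bands, the ratio will drift within a band and step at its edge, so the raw and scaled versions should be read together. The split does not replace a control arm.

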11.4.5. Primary Variables

11.4.5.1 *Adverse Event*

Adverse events will be classified using the MedDRA classification system. The severity of adverse events will be graded according to the CTCAE, Version 3.0, whenever possible.

A treatment-emergent adverse event is defined as an adverse event that occurs or worsens in severity in the period extending from the day of a subject's first ataluren dose in this study to 4 weeks after the last ataluren dose in this study.

The number and percentage of subjects experiencing a specific adverse event will be tabulated by body system and MedDRA term. A subject having the same event more than once will be counted only once. Adverse events will be summarized by worst CTCAE grade within a subject. Exposure-adjusted incidence rate will be reported.

Adverse events classified as CTCAE Grade 3 or higher; study-drug-related events; hepatic, and renal events leading to special diagnostic evaluations; events leading to discontinuation from treatment; SAEs; and AESIs will be considered with special attention.

11.4.5.2 *Laboratory Data*

Hematological, serum biochemistry, urine data, and their changes (only for continuous laboratory parameters) from baseline will be summarized descriptively for each visit. Hematological, serum biochemistry, and urine data will be graded according to CTCAE severity grade when applicable. For parameters for which a CTCAE scale does not exist, the frequency of subjects with values below, within, and above the normal ranges will be summarized. Summary tables will be presented for each relevant assay to show the number of subjects by severity grade with corresponding percentages. Subjects will be characterized only once for a given assay, based on their worst severity grade observed during the time period of interest.

Separate listings and tables will be created for assessment of hepatic and renal parameters.

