In the Phase 3 clinical trial (Study 009), serious adverse events related to renal dysfunction, which occurred only in the ataluren arm, included 3 patients with acute renal failure, 3 patients with renal failure, and 1 patient with hypercreatininemia. These events were characterized by elevated creatinine (Grade 1 to Grade 4), which resolved over days to weeks. Only 1 patient experienced symptoms of renal dysfunction (transient oliguria). All 7 events were associated with concomitant systemic treatment with potentially nephrotoxic antibiotics (eg, aminoglycosides, vancomycin) that were generally administered as treatment for pulmonary exacerbations. No patient required dialysis. One patient was unblinded and 1 patient chose not to continue study drug treatment; the remaining 5 of 7 patients restarted study medication and continued study participation without recurrent creatinine elevations. This issue was recognized during the conduct of the study and changes were made in the protocol (eg, prohibition of concomitant use of potentially nephrotoxic agents), which successfully addressed the issue.

Non-serious creatinine elevations occurred predominantly in the ataluren arm and were transient, generally mild, and resolved with or without interruption of study medication. The incidence of treatment emergent nephrolithiasis was similar in the ataluren and placebo groups.

Non-serious episodes of creatinine elevation in Study 009 occurred predominantly in the ataluren arm and were transient, generally mild, and resolved with or without interruption of study medication. However, there was no clinically meaningful difference in creatinine between the ataluren and placebo arms at Week 48, indicating that there was no cumulative effect of these transient elevations on renal function. The incidence of treatment-emergent nephrolithiasis was similar in the ataluren and placebo groups.

The renal monitoring program included in this protocol considers nonclinical and clinical findings with ataluren and past experience with known nephrotoxicants. Concomitant use of potentially nephrotoxic antibiotics with ataluren is prohibited. A focus is placed on well-established clinical indictors of renal dysfunction for making diagnostic decisions and prompting treatment interruptions/ modifications in individual patients. The rationale for each of the decision-making parameters is discussed below.

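### SAP 4.10.2 limits the worst-grade laboratory table to seven parameters, in action bands that merge creatinine Grades 2 to 4, and SAP 6 does not record this change from the protocol

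*SAP*

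**What the plan says.** Severity is part of the primary endpoint in both documents, for adverse events and for laboratory abnormalities (Protocol 3.3, SAP 2.3.1).

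Protocol 11.4.5.2 has haematology, biochemistry and urine results graded by CTCAE where a scale applies. It then states: "Summary tables will be presented for each relevant assay to show the number of subjects by severity grade with corresponding percentages". Each subject is counted once per assay, "based on their worst severity grade observed during the time period of interest". It closes by promising separate listings and tables for hepatic and renal parameters.

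SAP 4.10.2 repeats the once-per-subject, worst-grade rule but attaches it to a different table, one for the safety monitoring parameters only, which is "to show the number and percentages of subjects by severity grade categories defined in Table 2". SAP Table 2 holds seven parameters: total bilirubin, ALT, AST, GGT, cystatin C, creatinine and BUN. Creatinine has two bands, "Grade 1 (>ULN – 1.5 x ULN for age)" and "≥ Grade 2 (≥1.5 x ULN for age)".

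The same SAP section also plans a second graded output: "Shift tables for hematology, serum biochemistry, and urinalysis will also be presented showing change in CTCAE severity grade from baseline to each visit".

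SAP 6 lists the changes from the protocol and does not mention the laboratory tables. SAP 1 says that the SAP prevails where the two documents conflict.

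**The concern.** The bands in Table 2 were written to tell investigators when to stop drug and start a work-up. Used as reporting categories, they remove distinctions that a severity table exists to show. For creatinine, the distinction removed is the one this programme most needs. The protocol's overview and its section 15.3 describe Grade 3-4 creatinine elevations with ataluren in Study 009, linked to systemic nephrotoxic antibiotics. Protocol 14.2.4 says of the serious renal events: "These events were characterized by elevated creatinine (Grade 1 to Grade 4), which resolved over days to weeks".

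This extension runs with restrictions on those antibiotics. A reader of the study report will want to know how many subjects still reached Grade 3 or 4. The natural place to look is a laboratory table of subjects by worst grade. The protocol planned one, the SAP does not, and because the SAP prevails the protocol's table is no fallback.

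**Working it through.** The plan states no figure on this point, so there is none to reproduce. The check compares the two documents and then asks what each remaining output can show.

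**1. What the bands keep apart (SAP Table 2).**

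| Parameter | Bands | Lost |
|---|---|---|
| Creatinine | Grade 1; Grade 2 and above | Grades 2, 3 and 4 merged |
| Bilirubin, ALT, AST, GGT | Grade 2; Grade 3 and above | Grades 3 and 4 merged; no Grade 1 band |
| Cystatin C, BUN | thresholds without grades | not graded in Table 2 |

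Only five of the seven parameters carry grades. Gradable assays outside Table 2 have no worst-grade table.

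**2. What the merged creatinine cell can hide (illustrative counts).** Take three sets of worst-grade counts (Grade 2, Grade 3, Grade 4):

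- (7, 0, 0): Table 2 shows 7; Grade 3-4 is 0
- (4, 2, 1): Table 2 shows 7; Grade 3-4 is 2 + 1 = 3
- (0, 3, 4): Table 2 shows 7; Grade 3-4 is 3 + 4 = 7

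With about 200 patients (Protocol 5.1), the same cell is compatible with 0/200 = 0% up to 7/200 = 3.5%. With the SAP 2.4 upper bound of about 279, the range is 0% to 7/279 = 2.5%.

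A graded table showing no subject at Grade 3-4 would support an exact two-sided 95% upper limit of 1 − 0.025^(1/200) = 1.8%, or 1 − 0.025^(1/279) = 1.3%. SAP 4.1 already asks for 95% intervals on percentages.

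**3. What the shift tables can show.** They count subjects at Grade 3 and at Grade 4 for every graded assay, but one visit at a time. Two subjects at Grade 3 on one visit each and one subject at Grade 3 on two visits give the same total across tables, so the tables cannot be added to a number of distinct subjects.

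SAP 5.2 takes analysis visits as the scheduled visits, without windows, and these are 12 weeks (84 days) apart. If onset is uniform between visits, the chance that an elevation lasting D days is present at a scheduled visit is D/84. The durations below are assumed, since the protocol gives only days to weeks:

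- D = 3: 3/84 = 3.6%
- D = 7: 7/84 = 8.3%
- D = 14: 14/84 = 16.7%
- D = 28: 28/84 = 33.3%

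For seven independent elevations of 14 days, the expected number seen at a visit is 7 × 14/84 = 1.2, and the chance of seeing none is (70/84)^7 = 28%. Protocol 7.1.2 asks for creatinine twice weekly or more during potentially nephrotoxic antibiotic courses, so many informative values will fall between visits.

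**4. What the adverse event tables can show.** SAP 4.10.1 counts subjects by system organ class, preferred term and worst grade, with separate tables for Grade 3 and above. The grade belongs to the reported event and is assigned by the investigator. The seven serious renal events in Study 009 were reported under three terms (3 acute renal failure, 3 renal failure, 1 hypercreatininemia; Protocol 14.2.4). Under Protocol 9.1.1, a laboratory abnormality that accompanies an already reported clinical event goes to source documents instead of becoming its own event.

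**5. Remaining outputs.** The SAP 4.10.1 renal listing for subjects above 1.5 × ULN is a listing of events, not a count by grade. Maximal change from baseline (SAP 4.10.2) is not expressed in grades.

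None of these outputs gives subjects by worst creatinine grade.

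**The case against.** The best reply is that severe creatinine elevations will be counted anyway, as adverse events. Table 2 calls for a stop and a work-up at Grade 2 and above. Protocol 9.1.1 makes an abnormality reportable once it needs investigation beyond a repeat test. Protocol 9.1.2 lists creatinine above the age-specific ULN as an event of special interest. If sites follow the protocol, a Grade 3-4 elevation should be a reported event or part of one, and SAP 4.10.1 counts it by grade.

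This largely stands. A reader might infer that Grade 3-4 creatinine goes uncounted, or that the study cannot say whether the signal persisted. The documents do not support that: the adverse event tables and the by-visit shift tables both count subjects at those grades. What the event route lacks is a single count based on measured values, because cases may be split across preferred terms and the grade is the investigator's grade for the event.

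A second reply is that the protocol never defines a relevant assay, so the SAP may simply be specifying it. That is possible. However, the sentence follows directly on the grading of all three laboratory panels, and hepatic and renal tables are promised separately, so the wider reading is more natural. Under either reading, merging grades departs from a table by severity grade.

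Two further inferences should be avoided. The loss cannot be expressed as a share of the analytes listed in SAP 4.10.2, because bilirubin appears there in three forms and the list does not say which analytes have a CTCAE scale. The rise in cholesterol and triglycerides in Protocol 15.3 is not a lost signal of this programme, because that paragraph concerns trials in nmDMD.

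**Conclusion.** The point holds as a gap in laboratory reporting and an undeclared departure from the protocol. SAP 4.10.2 confines the worst-grade count to seven parameters and to bands that merge creatinine Grades 2 to 4 and hepatic Grades 3 and 4. SAP 6 is silent on it. The planned laboratory tables therefore leave the number of subjects with worst creatinine at Grade 3 or 4 undetermined, anywhere from none to the whole of the merged cell.

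The consequence is moderate. The study is single-arm and descriptive, it was ended early, and the adverse event tables by grade recover much of the information. The case for change rests on severity being a named part of the primary endpoint and on this grade range being the known signal. The visit-overlap percentages depend on assumed durations of 3 to 28 days and uniform onset. The finding itself does not depend on them.

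**What to change.** In SAP 4.10.2, add a table for every assay with a CTCAE scale: number and percentage of subjects by worst post-baseline grade, with Grades 0, 1, 2, 3 and 4 shown separately. State that it uses all available values, scheduled and unscheduled; a table limited to scheduled visits would miss most short elevations. Keep the Table 2 band counts as an additional table. The drug-action thresholds themselves are not in question.

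The cost is one sentence and one table shell, since CTCAE grades are already needed for the shift tables. Grading must extend to unscheduled results. SAP 1 provides for amendment before database lock. If the sponsor prefers the narrower table, SAP 6 should list the change and give the reason.
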